### 11.3 Stopping Rules

#### 11.3.1 Part 1

If two out of six patients have a DLT at the lowest defined dose level (as defined in Section 4) attributable to the study therapy, the study will be stopped and re-evaluated.

#### 11.3.2 Part 2

A 20% rate of DLT will be considered acceptable and a 30% rate of DLT would be unacceptable. Monitoring for excess toxicity will take place quarterly. The trial will be

stopped if more than 3/9, 4/13, 5/17, 6/21, 7/26, 8/31, 9/36, 10/40, or 11/45 patients treated at the RP2D experience grade 3 or higher non-hematologic adverse events attributed to study therapy. The operating characteristics presented below were calculated using the R function “toxbdry” in the package “clinfun”. The output is from toxbdry(0.15, 0.4, 7:46, cP0 = 0.1, cP1 = 0.9, ngrid=6).

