Statistical Methodology	
Simon's optimal two-stage design will be used in Part 2. The primary outcome is the overall response rate (CR + PR) at 24 weeks. Withdrawal or progression prior to 24 weeks or missing 24-week assessment will be considered non-response. After the first 16 patients treated at the RP2D complete 24 weeks of therapy or meet treatment discontinuation criteria, enrollment will be put on hold and an interim analysis will be conducted. This study treatment will be considered promising if the overall response rate at 24 weeks is <math>\geq 60\%</math> and unacceptable if the overall response rate at 24 weeks is <math>\leq 40\%</math>. 50% is the reported best overall response rate of current first-line therapy with high-dose steroids. The null hypothesis that the true response rate is <math>\leq 40\%</math> will be tested against a one-sided alternative.
 
In the first stage of the dose-expansion study, 16 patients will be accrued and followed through the first 24 weeks of treatment. Of those 16 patients, 6 patients will be carried over from Part 1 at the RP2D. In recognition of a potential accrual pause of at least 24 weeks, if all 16 patients are required to complete six months of combination therapy, we will permit enrollment of an additional 3 patients (20%) after the first 10 eligible patients in the first stage of the dose-expansion study are enrolled if no more than 5 of 16 patients have experienced treatment failure (i.e. addition of secondary systemic therapy or disease relapse or death) by the end of week 12 of treatment. If there are 7 or fewer responses in the first 16 patients enrolled, the study will be stopped. Otherwise, 30 additional patients will be accrued for a total of 46. The null hypothesis will be rejected if 24 or more responses are observed in 46 patients. This design yields a type I error rate of 0.0486 and a power of 80% when the true response rate is <math>\geq 60\%</math>.
 
To protect patient safety, an early stopping rule for toxicity will be implemented in Part 2. A 20% rate of DLT will be considered acceptable and a 30% rate of DLT would be unacceptable. The trial will be stopped if more than 3/9, 4/13, 5/17, 6/21, 7/26, 8/31, 9/36, 10/40, or 11/45 patients experience grade 3 or higher non-hematologic adverse events attributed to study therapy. Response assessments will occur every month for the first 24 weeks. The primary efficacy endpoint will be evaluated at 24 weeks. Patients with responding disease may continue therapy for another 24 weeks.
 
Toxicity in this trial will be defined as DLTs as described in Section 4.3, attributed to the study therapy. A safety analysis will be conducted on the safety population, which includes enrolled

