**Table 11: Probability of stopping**

Operating characteristics of Stopping Rule			
Probability of DLT	Probability of Crossing Boundary	Probability of Stopping Before the Last Patient	Expected Sample Size
0.15	0.098	0.098	43.3
0.20	0.304	0.304	38.3
0.25	0.586	0.586	31.1
0.30	0.818	0.818	23.6
0.35	0.942	0.942	17.7
0.40	0.987	0.987	13.7

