### 12.4.2 Secondary Endpoint Analysis

#### Safety

Toxicity in this trial will be defined as Dose Limiting Toxicities identified in Section 4.3 attributable to the study therapy. If the observed rate of DLTs exceeds 30% during Part 2 portion, the trial will be stopped.

A safety analysis will be conducted on the safety population, which includes enrolled subjects who receive at least one dose of study drug (itacitinib) and one ECP treatment. The baseline value is defined as the last value collected on or prior to the first dose date of the study drug. The safety variables to be analyzed include exposure of the study drug, AEs, clinical laboratory test results, Karnofsky/Lansky performance status, physical examination, and vital sign measurements. In general, safety data will be tabulated or listed. Descriptive statistics will be used to tabulate toxicities.

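### The Part 2 toxicity stopping rule is calibrated in DLTs but counts a different event, and Section 12.4.2 adds a second, unlinked stop that gives different answers

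*Combined protocol and SAP*

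**What the plan says.** Section 11.3.2 opens with DLT rates: "A 20% rate of DLT will be considered acceptable and a 30% rate of DLT would be unacceptable". It then gives a boundary (more than 3/9, 4/13, 5/17, 6/21, 7/26, 8/31, 9/36, 10/40 or 11/45) and applies it to "patients treated at the RP2D experience grade 3 or higher non-hematologic adverse events attributed to study therapy". On timing it says "Monitoring for excess toxicity will take place quarterly". The operating characteristics come from the call "toxbdry(0.15, 0.4, 7:46, cP0 = 0.1, cP1 = 0.9, ngrid=6"), which looks after every patient from 7 to 46. The first column of Table 11 is headed "Probability of DLT".

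The synopsis repeats both halves. Its boundary counts "patients experience grade 3 or higher non-hematologic adverse events attributed to study therapy", yet it goes on: "Toxicity in this trial will be defined as DLTs as described in Section 4.3, attributed to the study therapy".

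Section 12.4.2 (Safety) also defines toxicity as Section 4.3 DLTs and adds: "If the observed rate of DLTs exceeds 30% during Part 2 portion, the trial will be stopped". It does not mention the 11.3.2 boundary. Section 4.1 refers safety monitoring to Section 11.3 only.

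**The concern.** The two events overlap but neither contains the other. Under Table 3 in Section 4.3:

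- DLTs include hematologic events, such as prolonged grade 4 neutropenia. The boundary leaves these out.
- DLTs include an adverse reaction that leads to dose reduction or withdrawal, with no grade stated. A grade 2 event of this kind is a DLT but does not count toward the boundary.
- DLTs exempt listed grade 3 non-hematologic events, such as short-lived fatigue. If attributed to therapy, these count toward the boundary.

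The time windows are not aligned either. Section 4.3 defines the DLT period (lead-in to cycle 1 day 28) for dose-finding, and nothing says whether it governs Part 2 monitoring. The boundary event has no stated window.

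The denominators also differ. Section 11.3.2 counts patients treated at the RP2D, which includes the six carried over from Part 1 (Section 12.1 includes them in the 46). Section 12.4.2 speaks of the Part 2 portion and does not say whether those six count.

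Section 16.3 has stopping rules summarised for the DSMC. As written, that committee has two mandatory stops that can disagree on the same data, and a table that does not describe either one by DLT rate.

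**Working it through.** **Inputs.** The boundary, the looks (7 to 46) and the quarterly schedule are from 11.3.2, the target figures from Table 11, the 30% stop from 12.4.2, and the maximum of 46 from 12.1.

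**Method.** Let f_n(k) be the probability of k events in n patients without having stopped:

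f_n(k) = (1 − p)·f_{n−1}(k) + p·f_{n−1}(k − 1)

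At each look n, the mass S_n with k at or above the stopping count is removed. P(stop) = ΣS_n, and expected N = Σ n·S_n + 46·(1 − ΣS_n).

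**Step 1: reproduce Table 11.** More than k is read as k + 1 or more, held flat up to each printed n: 4 for n = 7–9, 5 for 10–13, 6 for 14–17, 7 for 18–21, 8 for 22–26, 9 for 27–31, 10 for 32–36, 11 for 37–40, 12 for 41–45. The count at 46 is inferred as 13, because Table 11 shows no stopping at the last patient.

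| p | P(stop), recomputed | Table 11 | Expected N, recomputed | Table 11 |
|---|---|---|---|---|
| 0.15 | 0.0978 | 0.098 | 43.31 | 43.3 |
| 0.20 | 0.3036 | 0.304 | 38.31 | 38.3 |
| 0.25 | 0.5858 | 0.586 | 31.05 | 31.1 |
| 0.30 | 0.8185 | 0.818 | 23.63 | 23.6 |
| 0.35 | 0.9424 | 0.942 | 17.71 | 17.7 |
| 0.40 | 0.9869 | 0.987 | 13.68 | 13.7 |

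The table is correct for whatever event is counted, with a look after every patient. Its DLT label is what does not match.

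**Step 2: is the 30% stop the same rule in other words?** Exceeding 30% needs floor(0.3n) + 1 events; at n = 31, for example, floor(9.3) + 1 = 10.

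| n | Boundary stops at | Over 30% stops at |
|---|---|---|
| 9 | 4 | 3 |
| 13 | 5 | 4 |
| 17 | 6 | 6 |
| 21 | 7 | 7 |
| 26 | 8 | 8 |
| 31 | 9 | 10 |
| 36 | 10 | 11 |
| 40 | 11 | 13 |
| 45 | 12 | 14 |

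The rules agree at 17, 21 and 26 and differ at the other six sizes, by one or two patients. The 30% rule is stricter early (3/9 and 4/13 stop only under 12.4.2) and looser late (9/31, 10/36, 11/40 and 12/45 stop only under 11.3.2).

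**Step 3: both rules together.** Assume one common event, with the trial stopping at the lower of the two counts.

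| 30% rule applied | P(stop) at 20% | P(stop) at 30% |
|---|---|---|
| Not at all (Table 11) | 0.304 | 0.818 |
| Every patient from 7 | 0.432 | 0.865 |
| From 10 | 0.384 | 0.850 |
| From 16 | 0.343 | 0.835 |
| From 20 | 0.312 | 0.822 |

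With both rules checked only at the nine printed sizes, the figures are 0.419 and 0.859.

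**Step 4: quarterly looks, boundary alone.** The synopsis gives 2–3 years for Part 2, so 40 patients accrue at 40/12 = 3.3 to 40/8 = 5 per quarter. Assume looks start at patient 7.

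| Step | Last look | 20% | 30% | With a look at 46 added: 20% | 30% |
|---|---|---|---|---|---|
| 3 | 46 | 0.266 | 0.789 | 0.266 | 0.789 |
| 4 | 43 | 0.242 | 0.765 | 0.247 | 0.777 |
| 5 | 42 | 0.214 | 0.722 | 0.225 | 0.752 |

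If each review instead checks the boundary retrospectively, in patient order at the printed sizes, the crossing probabilities stay at 0.304 and 0.818, and quarterly timing only delays detection.

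**The case against.** The best defence is that one rule is clearly operative. Section 4.1 points only to 11.3, and the synopsis repeats the boundary but not the 30% stop. The 30% sentence appears once, under secondary endpoint analysis, and could be a loose echo of the 30% unacceptable rate. That is a fair account of the likely intent. But the sentence is an unconditional instruction to stop, nothing subordinates it, and step 2 shows that it is not a paraphrase. It also leaves the event mismatch within 11.3.2 untouched.

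The second line of defence concerns the magnitudes, and much of it stands. The 0.432 requires one common event, when the events in fact differ, and an early start for a rule that has no schedule. It also treats the first six patients as unselected, although Table 2 allows at most one DLT among them at the RP2D. If the common event is the DLT, conditioning on that (with the six counted in both rules and no later events among them) gives 0.182 for the boundary and 0.254 for both rules at 20%, and 0.689 and 0.731 at 30%. The second rule then adds about 0.07 at 20% (0.254 − 0.182), not 0.13 (0.432 − 0.304). Table 11 ignores this selection as well. The low end of the quarterly range, 0.722, comes from a schedule that never reviews the last four patients.

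It can also be argued that 12.4.2 imports the Section 4.3 window along with the definition. That reading is open but not settled, because 4.3 ties its window to dose-finding.

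Finally, Section 16.3 provides DLT notifications, monthly SAE review, quarterly DSMC review and power to stop. Hematologic DLTs would therefore still reach the monitors. The defect lies in the formal rule and its stated properties, not in an absence of oversight.

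**Conclusion.** The contradiction is in the current text and should be corrected. It does not depend on any of the modelled probabilities: the rates and Table 11 refer to DLTs, the boundary counts another event, and 12.4.2 imposes a separate stop that departs from the boundary at six of the nine printed sizes.

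The probability of stopping at a 20% or 30% DLT rate is therefore not known from the document. The effect of the event mismatch cannot be computed, because no shares of hematologic, exempted or low-grade events are given. The illustrations show how far the choice of rules and looks can move Table 11. With both rules on one event, stopping at 20% runs from 0.312 to 0.432 depending on when the 30% rule starts. With the boundary alone at quarterly looks from patient 7, every 3 to 5 patients, it is 0.21–0.27 at 20% and 0.72–0.79 at 30%. These rest on the assumptions stated with each.

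**What to change.** Amend the synopsis, 11.3.2, Table 11 and 12.4.2 so that the stated rates, the counted event, its Part 2 window, the denominator and the table label all refer to the same thing. State whether the 30% sentence in 12.4.2 is a separate rule, a description of 11.3.2, or to be removed. If both rules stay, give the 30% rule a minimum sample size and a look schedule, and say whether the six carried-over patients count in it. Recompute Table 11 for the rules and looks as they will be applied, including how a quarterly review uses the boundary. Which event and rule to keep is for the sponsor.

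The cost is wording in four places and possibly one recomputed table. No new data are needed, since adverse events are already graded and attributed (Section 16.4). The recomputed figures may look less favourable than those printed. Relabelling alone will not change the 0.304 chance of stopping at a 20% rate of the counted event.

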**Name of Institution**

**STUDY SUMMARY**

Title	A Phase 2 Study of Itacitinib (INCB039110) and Extracorporeal Photopheresis (ECP) for First-line Treatment in Chronic Graft-versus-Host Disease
Short Title	FLIGHT
Protocol Identifiers (IRB – internal)	HCI IRB #130090
IND number	IND # 151546
Phase	Phase 2
Design	This is a multisite, single-arm, open-label Phase II study of oral itacitinib in combination with extracorporeal photopheresis in subjects with moderate to severe chronic GVHD. Part 1 will utilize a standard 3+3 design to evaluate the safety of daily oral itacitinib in combination with ECP. Part 2 is an expansion phase and patients will be treated with itacitinib in combination with ECP to determine its clinical efficacy in the treatment of moderate-severe chronic GVHD.
Study Duration	
 
• Part 1: 6-18 months
 
• Part 2: 2-3 years
 

Study Center(s)	This study will be conducted at the Huntsman Cancer Institute and up to 3 additional cancer centers
Objectives	
Primary Objective:
 
 
• Part 1: To assess an appropriate dose of itacitinib in combination with Extracorporeal Photopheresis (ECP) in patients with moderate or severe chronic GVHD.
 
• Part 2: To assess the clinical efficacy of itacitinib in combination with ECP in subjects with moderate or severe chronic GVHD treated at the Recommended Phase 2 Dose (RP2D).
 
 
Secondary Objectives:
 
 
• To assess the safety of itacitinib in combination with ECP.
 
• To assess long term response and efficacy.
 

Number of Subjects	6 to 18 patients being evaluated in Part 1. 40 subjects enrolled in Part 2.
Diagnosis and Main Eligibility Criteria	
Key Inclusion Criteria:
 
 
• Active, clinically diagnosed, moderate or severe chronic GVHD as defined by the NIH Consensus Development Project Criteria.
 

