#### **16.4 Adverse Events**

An adverse event is the appearance or worsening of any undesirable sign, symptom, or medical condition occurring after starting the study drug even if the event is not considered to be related to study drug. For the purposes of this study, the terms toxicity and adverse event are used interchangeably. Medical conditions/diseases present before starting study drug are only considered adverse events if they worsen after starting study drug. Abnormal laboratory values or test results constitute adverse events only if they induce clinical signs or symptoms, are considered clinically significant or require therapy.

Collection of adverse events will begin with the initiation of study therapy and end 30 days after the last dose of study drug (or until new cancer treatment is initiated).

Information about all adverse events, whether volunteered by the subject, discovered by investigator questioning, or detected through physical examination, laboratory test or other means, will be collected, recorded and followed as appropriate.

The adverse event should be evaluated to determine:

1. The severity grade based on CTCAE v5.0 (grade 1-5)
2. Its relationship to itacitinib, ECP, GVHD, and transplant associated therapies (i.e. transplant, conditioning regimen, or immunosuppressants) (definite, probable, possible, unlikely, not related)
3. Its duration (start and end dates or if continuing at the final exam)
4. Action taken (no action taken; study drug dosage adjusted/temporarily interrupted; study drug permanently discontinued due to this adverse event; concomitant medication taken; non-drug therapy given; hospitalization/prolonged hospitalization)
5. Whether it constitutes an SAE

All adverse events will be treated appropriately. Such treatment may include changes in study drug treatment as listed in the dose modification section of this protocol (see Section 8 for guidance). Once an adverse event is detected, it should be followed until its resolution, and assessment should be made at each visit (or more frequently, if necessary) of any

changes in severity, the suspected relationship to the study drug, the interventions required to treat it, and the outcome.

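### Table 11 gives upper limits for how often the Part 2 toxicity rule stops the trial: it assumes instant outcomes and a look after every patient, and the written rule has neither

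*Combined protocol and SAP*

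**What the plan says.** Section 11.3.2 sets the target rates in DLT terms: "A 20% rate of DLT will be considered acceptable and a 30% rate of DLT would be unacceptable". The boundary itself counts a different event, namely how many "patients treated at the RP2D experience grade 3 or higher non-hematologic adverse events attributed to study therapy". The trial is to be "stopped if more than 3/9, 4/13, 5/17, 6/21, 7/26, 8/31, 9/36, 10/40, or 11/45 patients treated at the RP2D" have such an event. Timing is given in one sentence: "Monitoring for excess toxicity will take place quarterly". No event window or minimum follow-up is stated.

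Other sections bear on how long an event can take to appear:

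- Section 12.2.2 makes a patient evaluable for toxicity from the first itacitinib dose.
- Section 6.7 allows up to 12 cycles of therapy.
- Section 16.4 says: "Collection of adverse events will begin with the initiation of study therapy and end 30 days after the last dose of study drug".
- The Study Summary and Section 12.4.2 define toxicity as the DLTs of Section 4.3. Section 4.3 limits these to the lead-in plus cycle 1, and states that window for dose-finding.

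Table 11 lists the "Probability of Crossing Boundary", the probability of stopping before the last patient, and the expected sample size. They come from a toxbdry call with looks at n = 7 to 46.

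**The concern.** A patient who started yesterday adds one to the denominator and has had almost no time to add to the numerator. If attributed grade 3 or higher events arise over months of therapy, the rate seen at a look is below the rate the same patients will eventually show. Quarterly looks also let several patients enter between checks, whereas Table 11 checks after each one.

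Both effects push the same way: the rule stops less often and later than Table 11 states. The DSMC and IRB would be relying on protection that the written rule does not deliver, and more patients would be treated at a dose whose toxicity the protocol calls unacceptable.

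**Working it through.** **1. Reproduce Table 11.** Use an exact binomial recursion, one patient at a time, stopping when events exceed the step boundary (more than 3 for n = 7-9, more than 4 for n = 10-13, and so on), with each outcome known when the patient is counted. At true rates 0.15, 0.20, 0.25, 0.30, 0.35 and 0.40 this gives:

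- crossing probabilities 0.098, 0.304, 0.586, 0.818, 0.942, 0.987
- expected N 43.3, 38.3, 31.1, 23.6, 17.7, 13.7

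Every entry matches. Stopping at, rather than above, the boundary does not reproduce it (0.248 at 0.15; 0.915 at 0.30).

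**2. Direction.** At any n, events seen so far cannot exceed the eventual events in the same n patients. So a crossing with delayed events implies that the Table 11 calculation has crossed at that n or earlier. Looking less often can only remove crossings. This needs no assumption about accrual or event timing.

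**3. Size at one look, by hand.** Expected observed rate = p x mean of min(time on study / W, 1), where W is the period over which events spread uniformly. Assume 2 patients per month and no hold, at the moment patient 26 starts. Times on study are 0, 0.5, ..., 12.5 months.

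- W = 48 weeks (11.05 months): the 23 patients at 0 to 11 months contribute 126.5/11.05 = 11.45, and the other three contribute 3. Mean = 14.45/26 = 0.56. At p = 0.30 the observed rate is 0.17.
- W = 24 weeks (5.52 months): the mean is 0.77 and the observed rate is 0.23.

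Crossing at n = 26 needs 8 events, a rate of 8/26 = 0.31.

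**4. Size over the trial, by simulation.** Inputs:

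- Accrual (assumed): the Study Summary gives "Part 2: 2-3 years", and 40 patients in 36 or 24 months is 1.11 or 1.67 per month.
- Hold: 5.5 months after patient 16, approximating the 24-week efficacy interim in Section 12.1. It is added to the accrual time.
- Looks: quarterly. Denominator: patients treated. Event times: uniform over W.
- The efficacy futility stop is ignored, as in Table 11.
- With at least 6,000 trials per cell, the Monte Carlo standard error is at most sqrt(0.25/6000) = 0.006.

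Results at a true rate of 30%:

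| Event timing | Stops before last patient | Expected enrolled |
|---|---|---|
| Table 11 | 0.818 | 23.6 |
| Immediate, quarterly looks | 0.76-0.78 | 26-27 |
| Within about 5 weeks | 0.72-0.76 | 27-30 (at 1 to 2 per month) |
| Over 24 weeks | 0.61-0.67 | 31-33 |
| Over 12 months | 0.38-0.55 | 35-39 |

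**5. Sensitivity at 30%, quarterly looks.**

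- At 1, 2 and 3 patients per month: 0.69, 0.54 and 0.42 with a 24-week spread; 0.59, 0.32 and 0.18 with a 48-week spread.
- Early-loaded events over 12 months: 0.59-0.67 at 1.11 to 1.67 per month. At 2 per month, early-loaded events give 0.64 over 24 weeks and 0.52 over 48 weeks.
- Half the patients stopping at 24 weeks plus 30 days, against the 12-month case: 0.47-0.61.
- Crossing at any time, including after accrual ends: 0.65-0.76 across the 24- and 48-week runs at 1 to 3 per month, with continuous or quarterly looks.

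At a true rate of 40%, against 0.987 in Table 11, stopping before the last patient is 0.81-0.96 (24 weeks) and 0.53-0.92 (48 weeks) at 1 to 3 per month.

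**6. Would the DLT window cure it?** Take 38 days (a 10-day lead-in plus 28 days). If a 30% rate is spread over 12 months, that window sees 0.30 x 38/365 = 3.1%. If it is spread over 24 weeks, the window sees 0.30 x 38/168 = 6.8%. At those rates the exact recursion stops with probability about 0.0001 and 0.003.

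**The case against.** The strongest reply is that toxicity here means DLT. The target rates, the Table 11 column header, the Study Summary and Section 12.4.2 all use that term, and Section 4.3 gives it a window of about 5 weeks. On that reading delay costs only about 2 to 4 points beyond quarterly looks. This stands as a statement about size. It does not settle the rule, because Section 11.3.2 counts a different event without a window and Section 4.3 ties its window to dose-finding.

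Three further points stand in part:

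- The 12-month uniform case is severe. The Study Summary and Sections 4.1 and 6.1 tie treatment beyond 24 weeks to PR or better, although Section 6.7 is looser, and early-loaded events shrink the loss.
- The shortfall narrows as follow-up matures. At a true 40% rate, crossing at any time stays at 0.96-0.98, but by then most patients have been exposed.
- Section 16.3 provides SAE notification to the medical monitor, monthly SAE review and quarterly formal DSMC review. Section 12.4.2 adds a stop if the observed Part 2 DLT rate exceeds 30%. These are separate safeguards, but they do not make Table 11 correct.

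A reader might infer more than the documents support:

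- That the boundary was miscalculated. It was not; step 1 matches every entry.
- That delay explains the whole gap to 0.818. Quarterly looks account for part of it.
- That the loss is equally large whichever event is counted. Only the direction is common to all.
- That adopting the DLT window would be a nearly free repair. Step 6 shows that it would remove late events from the boundary.

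**Conclusion.** The point holds. For the rule as written, Table 11's stopping probabilities are upper limits and its expected sample sizes are lower limits. That follows from the text and needs no assumption.

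The size is conditional. At a true 30% rate, stopping before the last patient falls from 0.818 to somewhere between 0.76-0.78 (immediate outcomes, quarterly looks) and 0.38-0.55 (events spread over 12 months). Expected enrolment is about 26 to 39 against 23.6. These ranges rest on 1.11 to 1.67 patients per month, a 5.5-month hold and uniform event times, none of which the protocol states as planning values. Faster accrual enlarges the loss and early-loaded events reduce it.

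This should be corrected, because a stated property of the safety rule is not delivered. It does not show that patients lack oversight or that the boundary values are unusable.

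**What to change.** 1. Replace Table 11 with operating characteristics simulated for the rule as it will be run: quarterly looks, projected accrual, the enrolment hold after patient 16 and a stated range of event timing. Report stopping before the last patient and expected enrolment at the same six true rates.

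2. Reconcile the counted event. Section 11.3.2 uses attributed grade 3 or higher non-hematologic events, while the Study Summary and Section 12.4.2 use Section 4.3 DLTs. State one event, its observation window, and when a patient enters n.

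3. If a window is chosen, state its price. A window of about 5 weeks keeps the delay loss small for early events but takes later ones out of the boundary, so the protocol must say how those are reviewed. With a window-complete denominator, count patients in enrolment order. If the boundary is then checked patient by patient, Table 11's crossing probabilities apply by construction, although more patients may have been enrolled by the time it is crossed. Counting patients who have either completed the window or had the event brings events in ahead of non-events. With a 24-week or 12-month window this raises stopping at a 20% rate to about 0.32-0.41, against 0.304 in Table 11.

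The cost is one simulation, a replaced table, a few sentences in Section 11.3.2 and possibly a different count in the quarterly report. The sample size and the two-stage efficacy design are unchanged. The new table will probably show weaker early stopping than the current one, and the DSMC should see that before it relies on the rule.
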